4.13. PICO

P (participants): cancer patients requiring a percutaneous nephrostomy procedure, at the first catheter passage and at subsequent changes.

I (intervention): Use of empirical or uroculture-guided antibiotic prophylaxis.

C (comparisons): compare patients with and without antibiotic prophylaxis and, if used, empirical or guided by uroculture.

O (outcomes): urinary tract infection.

4.14. Registration of the Research Protocol

This systematic review will be duly registered in PROSPERO (*International Prospective Register of Systematic Reviews*), since there is no record of similar research currently being carried out in this database.

4.15. Research Protocol

The protocol for the literature search will be based on the population of cancer patients requiring percutaneous nephrostomy (at the first catheter passage and subsequent changes), whose intervention will be the use of empirical or uroculture-guided antibiotic prophylaxis to compare patients with and without the use of antibiotic prophylaxis and, if used, empirical or uroculture-guided, with urinary tract infection as the outcome.

This systematic review will follow the suggestions dictated by the PRISMA recommendations (*Preferred Reporting Items for Systematic Reviews and Meta-analyses*)⁴⁸ during its process of acquiring and synthesizing the evidence.

4.16. Database search strategy

The systematic literature search will use the PubMed (MEDLINE), Cochrane and EMBASE databases and will be carried out comprehensively and will start from May 1, 2021 until August 1, 2021.

To obtain the evidence, the literature will be researched using the terms "*nephrostomy, percutaneous*" in combination with "*antibiotic prophylaxis*", "*urinary tract infection*"; "*ureteral obstruction*" and "*neoplasms*". The references of the studies found in the systematic review will be evaluated in order to identify more relevant studies for this research.

4.17. Variables to be studied

From the studies found, available data will be extracted relating to the number of cancer patients undergoing percutaneous nephrostomy, type of nephrostomy (first pass, catheter exchange or undefined), neoplastic diseases that led to ureteral obstruction, whether or not antibiotic prophylaxis was taken before, during or after the procedure and the occurrence of urinary tract infection after the procedure, regardless of the date.

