1.5.2. The question of antibiotics

Antibiotic prophylaxis in surgical procedures follows certain principles:

It is a brief administration of antibiotics before or at the beginning of an intervention used to minimize infectious complications related to diagnostic or therapeutic intervention. Even though its use is widely accepted, there are risks of side effects and the development of multidrug-resistant microorganisms ^{31, (32)}.

The potential benefit is determined by three conditions: patient-related factors (ability of the host to respond to bacterial invasion); procedure-related factors (likelihood of bacterial invasion at the surgical site) and the potential morbidity of the infection ⁽³²⁾.

It is only recommended when the potential benefits exceed the premeditated costs and risks ⁽³²⁾.

The antimicrobial agent used must be effective against the bacterial microorganism characteristic of the surgical site relevant to causing infectious disease, also considering the cost, convenience and safety of the antibiotic ⁽³²⁾.

Its duration should be for the period in which bacterial invasion is facilitated and/or likely to establish an infection ⁽³²⁾.

According to the *American Heart Association*, antimicrobials are no longer recommended in genitourinary procedures solely to prevent infective endocarditis as this is not an effective strategy. Infective endocarditis occurs as a result of random bacteremia associated with daily activities and not due to genitourinary procedures ^{32, (33)}.

However, it is only indicated against α -hemolytic streptococci in patients at high risk of developing infective endocarditis (patients with valve prostheses, previous history of infective endocarditis, congenital heart disease treated with material considered to be a foreign body or heart transplant with valvulopathy) and the use of amoxicillin or cefazolin is recommended ^{33, (34)}.

Based on these principles, antibiotic prophylaxis in urological procedures is an important and easily modifiable preventive measure to reduce postoperative infections. The decision to carry it out and the selection and dose of the antibiotic to be used can

be based on consensus, but a comprehensive assessment of the patient's specific circumstances should also be considered ⁽³²⁾.

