1.5.2.2. Interventional radiology consensus

The consensus on antibiotic prophylaxis in procedures performed by interventional radiologists are the ones that most often mention percutaneous nephrostomy. These documents also define colonization as the presence of a microorganism without leading to a systemic inflammatory response^{34, (42)}.

They recommend the use of antibiotic prophylaxis for all patients, except for catheter changes in non-infected cases, without obstruction and in immunocompetent patients because there is no description in the literature, but also, without guarantees, with levels of evidence ranging from historical, non-randomized or case-control studies to case series without control group, with limited data and expert opinions (grade of recommendation IIb, with level of evidence in limited data and expert opinion)^{34, (42)}.

Brick *et al.* retrospectively evaluated 493 percutaneous nephrostomy catheter exchange procedures carried out on 126 patients, 213 procedures before a change in clinical practice and 280 procedures after this change which consisted of not carrying out antibiotic prophylaxis on patients considered to be at low risk of infection, as suggested by the consensus described above. High risk was considered to be the presence of 2 to 5 risk factors and low risk 0 to 1 of these factors, which were type II diabetes, previous urinary tract infection, history of neoplasm or obstruction, hypertension and kidney transplantation. Using the risk stratification model used, the authors concluded that changing the prophylaxis practice used had no effect on the rate of hospital admission due to infection or on the rate of infection in outpatients, corroborating that not using antibiotic prophylaxis for routine catheter changes in patients at low risk of infection does not increase the rate of infection⁽²⁷⁾.

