4.18. Inclusion Criteria

- Entire studies in English;
- No limitations on dates or type of studies (if no clinical trials are found, observational studies will be used);
- Studies showing the relationship between urinary tract infection and antibiotic prophylaxis after percutaneous nephrostomy in cancer patients, even if they contain data on benign obstructive ureteral diseases.

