4.22. Statistical analysis

The meta-analysis will be carried out using the *Comprehensive Meta-Analysis* software version 2⁽⁴⁹⁾. At this stage, we will use heterogeneity tests together with Funnel Plot and Forrest Plot graphical analyses.

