4.23. Methodological quality and risk of bias assessment

As noted when this research project was conceived, no randomized studies on the subject had been found so far. Thus, to assess the quality of the studies to be researched and the risk of bias, the ROBINS-I tool (Risk Of Bias In Non-randomized Studies - of Interventions) will be used⁵⁰. This tool provides a comprehensive and structured approach to evaluating non-randomized studies of interventions, providing a complete assessment of the risk of bias in relation to a hypothetical randomized clinical trial. It is divided into 7 domains, two pre-intervention domains (confounding bias and participant selection bias within the study), one in-intervention domain (bias in the classification of interventions) and four post-intervention domains (bias from deviations in intended interventions, bias from missing data, bias in the measurement of outcomes and bias in the selection of the reported outcome). The evaluation of each study will be divided into six stages: specify the research question in consideration of a target study; specify the outcome and result being evaluated; for the specified result, examine how confounding factors and co-interventions were addressed; answer the signaling questions for the seven domains of bias; formulate judgments of risk of bias for each of the seven domains informed by the signaling questions; and formulate an overall judgment about the risk of bias for the outcome and results being evaluated⁵⁰. This instrument can be found in full in Appendix III.

If randomized studies are found, the tool used will be recommended by the *Agency for Healthcare Research and Quality, Cochrane Collaboration*⁽⁵¹⁾.

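### The systematic review extracts no adjusted estimates or infection-risk factors and groups post-procedure antibiotics with prophylaxis, so its pooled result is at risk of confounding by indication and of exposure misclassification

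*Protocol*

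**What the plan says.** Protocol 4.17 lists the data to be taken from each study. Besides the number of patients, the list has "type of nephrostomy (first pass, catheter exchange or undefined), neoplastic diseases that led to ureteral obstruction", and then "whether or not antibiotic prophylaxis was taken before, during or after the procedure and the occurrence of urinary tract infection after the procedure". Infection counts "regardless of the date". Adjusted effect estimates, the covariates behind them and patient-level infection-risk factors are not listed.

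Protocol 4.18 accepts any design and adds that "if no clinical trials are found, observational studies will be used". Section 4.23 reports that "no randomized studies on the subject had been found so far" and plans ROBINS-I, which includes a confounding domain, for each non-randomised study.

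On synthesis, 4.22 names the software and says "we will use heterogeneity tests together with Funnel Plot and Forrest Plot graphical analyses". It gives no effect measure, pooling model, subgroup or sensitivity analysis. The SAP describes the cohort analysis and says nothing about the meta-analysis.

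Section 1.5.2 defines antibiotic prophylaxis as follows: "It is a brief administration of antibiotics before or at the beginning of an intervention".

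**The concern.** The review serves the primary objective jointly with the cohort (Protocol 3.1). If the studies are observational and only counts of exposure and infection are collected, the natural product is a pool of unadjusted comparisons.

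The protocol gives reasons to expect exposed and unexposed patients to differ in risk:

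- Section 1.5.2 says the decision on prophylaxis should take account of the individual patient. It also reports a 1991 study suggesting that prophylaxis may be omitted in patients at low risk of sepsis.
- Section 1.5.2.2 describes consensus documents that exempt only certain lower-risk catheter changes. It also describes a practice change that consisted of "not carrying out antibiotic prophylaxis on patients considered to be at low risk of infection".
- Section 1.5.2.3 names previous UTI and neutropenia as the main risk factors in a cancer cohort. Section 4.17 extracts neither.

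If higher-risk patients receive prophylaxis more often, an unadjusted comparison understates its benefit and can make a useful intervention look ineffective.

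A second, separate problem is exposure classification. An antibiotic started after the procedure may be treatment of an infection that has already begun. Counting it as prophylaxis makes infection a cause of exposure. The open-ended infection window adds to this; the cohort, by contrast, uses 7 days (4.10.2, 4.10.3).

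**Working it through.** The plan states no target effect, power or expected pooled estimate for the meta-analysis, so there is no figure to reproduce. The calculations below are illustrations. Their inputs are assumptions except where a source is given.

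**1. Confounding, odds-ratio scale.** Assume a true OR of 0.5 in each risk group, half of the patients at high risk, and prophylaxis given to 80% of high-risk and 20% of low-risk patients. The exposed are then 80% high-risk and the unexposed 20% high-risk.

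Risk with prophylaxis in a group = 0.5 × odds ÷ (1 + 0.5 × odds), where odds = p ÷ (1 − p) and p is the untreated risk.

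*Untreated UTI 20% (high) and 10% (low):*
- With prophylaxis: 11.1% and 5.3%.
- Exposed: 0.8 × 11.11% + 0.2 × 5.26% = 9.94%.
- Unexposed: 0.2 × 20% + 0.8 × 10% = 12.0%.
- Crude OR = (0.0994 ÷ 0.9006) ÷ (0.12 ÷ 0.88) = 0.81.

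*Untreated UTI 30% and 10%:*
- With prophylaxis: 17.6% and 5.3%.
- Exposed: 0.8 × 17.65% + 0.2 × 5.26% = 15.17%.
- Unexposed: 0.2 × 30% + 0.8 × 10% = 14.0%.
- Crude OR = (0.1517 ÷ 0.8483) ÷ (0.14 ÷ 0.86) = 1.10.

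The same formula with other allocations (true OR 0.5 throughout):

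| High-risk share, exposed/unexposed | Crude OR, 20% vs 10% | Crude OR, 30% vs 10% |
|---|---|---|
| 50/50 | 0.51 | 0.52 |
| 60/40 | 0.59 | 0.66 |
| 70/30 | 0.69 | 0.85 |
| 80/20 | 0.81 | 1.10 |

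The small departure from 0.5 in the 50/50 row arises because the odds ratio is not collapsible; it is not confounding.

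**2. The same check on the risk-ratio scale.** Crude RR = R × [h1·pH + (1 − h1)·pL] ÷ [h0·pH + (1 − h0)·pL]. R is the true RR, pH and pL are the untreated risks, and h1 and h0 are the high-risk shares among exposed and unexposed. With R = 0.7, h1 = 0.7, h0 = 0.3 and pL = 10%:
- pH = 15%: 0.7 × 13.5% ÷ 11.5% = 0.82.
- pH = 20%: 0.7 × 17% ÷ 13% = 0.92.
- pH = 30%: 0.7 × 24% ÷ 16% = 1.05.
- Equal shares: 0.70, so no bias.

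**3. Post-procedure antibiotics.** Take two equal groups of 100 with the same UTI risk of 11.4%, the institution's rate after catheter changes in 1.5.2.3, so the true RR is 1.0. Suppose a fraction of the infected unexposed patients are counted as exposed because their antibiotic came after the procedure.
- 10% moved (1.14 patients): (12.54 ÷ 101.14) ÷ (10.26 ÷ 98.86) = 1.19.
- 30% moved (3.42 patients): (14.82 ÷ 103.42) ÷ (7.98 ÷ 96.58) = 1.73.

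**4. Sections side by side.** Section 1.5.2 places prophylaxis before or at the start of the intervention; 4.17 admits it afterwards. No section says how timing would be used in the analysis or how treatment would be told apart from prophylaxis.

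**The case against.** Several counter-arguments have force.

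- **Confounding is not ignored.** ROBINS-I requires a judgement on it for every study. That stands as far as it goes, but it rates the estimate without changing it, and no section links the ratings to the pooling.
- **The extraction is not purely of exposure and outcome.** Nephrostomy type and neoplasm allow limited stratification. They do not allow it by previous UTI, neutropenia or diabetes.
- **Section 4.22 names no effect measure.** Crude pooling is therefore inferred from the extraction list. The inference is fair, because an adjusted estimate that is not extracted cannot be pooled.
- **Allocation by risk is not shown for every study.** The practice-change study is a before-and-after comparison. The 1991 study has patients with and without prophylaxis in both risk groups. The fever study in 1.5.2.3 gave prophylaxis in both groups and varied only its timing. This is why the point is a risk of bias and not a demonstrated bias.
- **Some post-procedure use is genuine prophylaxis**, as in that fever study, and 4.17 can be read as recording timing. This argues for a separate category rather than discarding the data.

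A reader might go further and infer that the bias would reverse the result, by combining the 1991 study's untreated sepsis rates (50% and 14%) with an assumed OR of 0.5. The documents do not support that. The same paragraph of 1.5.2 gives treated rates of 9% and 10%. With the 80/20 mix, all four rates give 0.8 × 9% + 0.2 × 10% = 9.2% against 0.2 × 50% + 0.8 × 14% = 21.2%, a crude OR of 0.38. An equal mix gives 9.5% against 32%, an OR of 0.22, so the benefit is attenuated but not reversed. These are also sepsis rates, and the protocol says they cannot be compared with other clinical situations.

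Nor do the documents establish that both problems must work against prophylaxis. The institution's own crude catheter-change rates in 1.5.2.3 (21.4% with none, 14.8% empirical, 6.4% targeted; p = 0.146) lean the other way.

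**Conclusion.** The point holds as a gap in the plan. If 4.17 and 4.22 are followed as written, the pooled estimate will rest on unadjusted data from studies expected to be non-randomised, and it is at risk of confounding by indication. The size, and even the presence, of the bias in the eventual pool cannot be known from the documents. Under an assumed true OR of 0.5, the crude OR runs from 0.59 to 1.10 across the unequal allocations and two baseline-risk contrasts tried. An equal risk mix leaves no confounding.

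The timing problem is a distinct one of exposure classification or reverse causation. Under the assumed 10% to 30% recoding, a null effect would appear as an RR of 1.19 to 1.73. Whatever its size, 1.5.2 and 4.17 contradict each other and must be reconciled.

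It would go too far to say that the pooled result will certainly be biased, that its direction will be reversed, or that the review disregards confounding.

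**What to change.** 1. Add to the 4.17 extraction list: the adjusted effect estimate with its confidence interval and covariates, or risk-stratified counts where a study gives them; the timing of the antibiotic relative to the procedure; and the infection follow-up window used.
2. In 4.22, name one common effect measure. Pool adjusted or stratified estimates by random-effects inverse variance where available. Show crude pooling alongside, split by ROBINS-I confounding rating, so that those ratings have a stated use.
3. Reconcile 4.17 with the definition in 1.5.2. For the analysis, code post-procedure antibiotics as a separate category, kept out of the main prophylaxis yes/no contrast.

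The cost is a few extraction columns and one extra forest plot. The downside is that few studies may report adjusted estimates, so that pool may be small and imprecise; the crude results shown beside it keep the remaining evidence visible.

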1.5.2.3. Antibiotic prophylaxis for percutaneous nephrostomy in cancer patients

Few studies have evaluated this issue in the context of percutaneous nephrostomy and malignant ureteral obstruction. One of them evaluated the role of antibiotic prophylaxis in urological procedures, with percutaneous nephrostomy performed in 15.3% of patients with both benign and malignant ureteral obstruction. The patients were followed up for 30 days after the procedure, and the only event studied was the presence of fever²⁶. Antibiotic prophylaxis was carried out in two ways, in the first group 30 minutes before the procedure and in the second group immediately after the procedure. Feverish complications occurred in 4.5% of both groups and in all procedures (ureteral catheters, nephrostomy and retrograde pyelography), with no statistical difference. The authors found that pyuria before the procedures and the degree of hydronephrosis were risk factors for urinary infection, and that antibiotic prophylaxis may be more beneficial in these situations⁽²⁶⁾.

Another retrospective study evaluated antibiotic prophylaxis and urinary infection after the first nephrostomy catheter passages for urinary tract clearance and after catheter changes in the oncology population. Fifty-one percent of the patients studied underwent nephrostomy catheter replacement. Patients were followed up for 90 days and 19% had catheter-related pyelonephritis and 7.5% had asymptomatic bacteriuria after the first passage³. Half of the patients who had pyelonephritis developed the infection one month after catheter insertion. Of the patients who had their catheters changed, 4% developed pyelonephritis and 2% asymptomatic bacteriuria. The authors concluded that the rate of pyelonephritis related to nephrostomy catheter insertion is relatively high, mainly due to gram-positive germs, with previous urinary tract infection and neutropenia being the main risk factors. The authors also concluded that antibiotic prophylaxis does not prevent nephrostomy catheter-related pyelonephritis, suggesting that the main risk factor for this infection is simply the existence of tumor disease⁽³⁾.

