A retrospective cohort carried out at this institution evaluated 180 percutaneous nephrostomies (87 first passes and 93 catheter changes) over a 3-year period. The occurrence of urinary tract infection related to the nephrostomy catheter was verified up to 7 days after the procedures, with 1.2% of urinary tract infection related to the nephrostomy catheter being identified after its first passage and 11.4% after catheter changes ($p = 0.01$)⁴³. In the first passages, there was no statistically significant difference in urinary infection rates when the patient received antibiotic prophylaxis or

not (0% *versus* 1.5%, respectively; $p = 0.999$). In catheter changes, even without statistical significance ($p = 0.146$), the urinary infection rate was 21.4% in those patients who did not receive antibiotic prophylaxis; 14.8% in those who received empirical antibiotic prophylaxis and 6.4% in those who received targeted antibiotic prophylaxis (with antibiotics guided by a previously collected uroculture result)⁴³. Despite the potential bias in results due to its retrospective nature, this study demonstrates a reality in clinical practice and also a possible solution both to prevent urinary infections in this population and to help rationalize the use of antibiotics.

Finally, a prospective study assessed the incidence of urinary tract infection after nephrostomy catheter changes without antibiotic prophylaxis and found that out of 126 catheter change procedures, 13.5% had infectious complications. Just over half (52.9%) required antibiotic treatment and only 1 patient was hospitalized for such treatment, but without threatening the patient's life, according to the authors⁽⁴⁴⁾.

Consequently, there are more doubts than certainties about antibiotic prophylaxis in percutaneous nephrostomy in cancer patients.

Based on what has been said so far, two fundamental questions can be posed. Firstly: would it be necessary to carry out antibiotic prophylaxis for the first passage of the percutaneous nephrostomy catheter to prevent urinary infection related to the procedure? And secondly: can uroculture-guided antibiotic prophylaxis be superior in preventing urinary tract infection when compared to empirical antibiotic prophylaxis after percutaneous nephrostomy catheter changes guided by imaging? These are the questions that guide this research project.

2.

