3. OBJECTIVES

3.1. Primary

- To evaluate the rate of urinary tract infection related to the percutaneous nephrostomy procedure in cancer patients, according to the use of antibiotic prophylaxis at the first catheter passage and subsequent changes, a retrospective cohort and systematic review with meta-analysis will be conducted.

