3.2. Secondary

- Describe the frequency of urinary tract infection related to the percutaneous nephrostomy catheter that occurs between catheter changes (not related to the procedure, but possibly to colonization of the catheter);
- To describe and compare the results of the urocultures involved in the study, as well as their sensitivity to the antibiotics used;
- Describe the main signs and symptoms involved in urinary tract infection related to the procedure and the nephrostomy catheter;

- Assess the severity of urinary tract infections according to the type of treatment and the need for hospitalization.
- To determine the risk factors for urinary tract infection related to the passage and subsequent changes of nephrostomy catheters.
- Describe the rates of urinary infections and associated germs according to the time of nephrostomy passage, first passage or catheter change.
- Report whether these catheters were changed when the urinary tract infection occurred and on which day after the urinary tract infection was diagnosed.

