4.10.2. First pass procedure

This group will be made up of patients who have undergone percutaneous nephrostomy for urinary tract clearance and we will study whether or not antibiotic prophylaxis was recorded in the medical records to be reviewed at these hospitals.

The following laboratory tests will be considered: serum creatinine and urea levels, urine samples for tests such as urine summary (or type I urine) and uroculture with antibiogram.

The proportion of urinary tract infections that developed within 7 days of the procedure will be studied. A procedure-related urinary tract infection is considered to be any report in the medical record of clinical signs and symptoms associated with uroculture results (see definition in item 4.10.4.) and the location of the respective treatment will be documented: outpatient, inpatient or intensive care unit (ICU).

It will be documented whether there is evidence reported in medical records of urinary tract infections or the presence of bladder fistulas prior to the procedure.

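### The review counts infection at any time after nephrostomy and does not record follow-up length, so its pooled estimate can mix two outcomes that the protocol keeps apart

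*Protocol*

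**What the plan says.** The primary objective (Protocol 3.1) is a single one, to be met by the cohort and the systematic review together: "To evaluate the rate of urinary tract infection related to the percutaneous nephrostomy procedure in cancer patients".

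The cohort gives this outcome a window. In 4.10.2, and in the same terms in 4.10.3: "The proportion of urinary tract infections that developed within 7 days of the procedure will be studied". Infections between catheter changes are a separate secondary outcome (3.2), described as "not related to the procedure, but possibly to colonization of the catheter". The definitions in 4.10.1 and 4.10.4 keep the same division.

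The review does not. Its PICO (4.13) names urinary tract infection without qualification, and its extraction list (4.17) takes "the occurrence of urinary tract infection after the procedure, regardless of the date". The phrase concerns when the infection occurred, since publication date is dealt with separately in 4.18. Neither follow-up length nor the study's definition of infection is on the list. The meta-analysis section (4.22) mentions heterogeneity tests, funnel plots and forest plots. It gives no effect measure, no pooling model and no analysis by window. The SAP has no section on the meta-analysis.

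**The concern.** The review could follow 4.17 to the letter and still not estimate the outcome that 3.1 sets for it. An infection in the first week and one two months later would count alike, although the protocol attributes them to different causes. The pooled figure could then not be laid directly beside the 7-day cohort result, which is the purpose of the combined design.

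There may also be a consequence for the size of the effect. Section 1.5.2 says of prophylaxis: "It is a brief administration of antibiotics before or at the beginning of an intervention". If such a dose acts mainly on early infections, counting later ones adds similar numbers to both groups and pulls a ratio towards 1.

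**Working it through.** The documents give no power, effect size or pooled estimate for the meta-analysis, so there is no planned figure to reproduce.

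**1. Are mixed windows a realistic prospect?** These are the studies described in 1.4.3 and 1.5.2.3:

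- 7 days: the institution's earlier cohort, of which 1.5.2.3 says "The occurrence of urinary tract infection related to the nephrostomy catheter was verified up to 7 days after the procedures". It reports infection by prophylaxis group.
- 30 days: a study that recorded fever only and gave prophylaxis to both groups, at different times.
- 90 days: an oncology cohort with pyelonephritis in 19% after first passage, which draws a conclusion on prophylaxis.
- 100 days: a study of catheter-related infection for which no prophylaxis comparison is described.

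The 7-day and 90-day studies are plausible inclusions, so the firm range is 7 to 90 days.

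**2. Dilution of a ratio.** Let f be the share of control-group infections that fall in the early window. Assume prophylaxis multiplies early risk by RR_early and leaves later risk unchanged. Then

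RR_observed = f × RR_early + (1 − f).

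RR_early is not in the documents. I take 0.50 as the central value and 0.30 to 0.70 as the range.

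| f | RR_early 0.30 | RR_early 0.50 | RR_early 0.70 |
|---|---|---|---|
| 0.50 | 0.65 | 0.75 | 0.85 |
| 0.25 | 0.825 | 0.875 | 0.925 |
| 0.06 | 0.96 | 0.97 | 0.98 |

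The early share f is not given either. The upper value of 0.50 leans on a sentence about the 90-day cohort: "Half of the patients who had pyelonephritis developed the infection one month after catheter insertion". Its wording is ambiguous, and it describes all patients, not an untreated group. The lower value is 1.2/19 = 0.063, which sets the 7-day first-passage rate of one study over the 90-day rate of another. That quotient is not an estimate of f. For catheter changes the same two studies run the other way, with 11.4% at 7 days against 4% in the 90-day study.

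**3. Effect on precision.** Take 19% as the control risk at 90 days (an assumption, since it is a cohort-wide rate), RR_early = 0.50, two-sided 5% and 80% power. With p0 and p1 the two risks and p̄ their mean,

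n per group = [1.96√(2p̄(1−p̄)) + 0.84√(p0(1−p0) + p1(1−p1))]² / (p0 − p1)².

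- f = 0.50: early events 9.5% v 4.75%, n = 460; any-date events 19% v 14.25%, n = 964.
- f = 0.25: early events 4.75% v 2.375%, n = 955; any-date events 19% v 16.625%, n = 4,074.

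The risk difference is the same on both counts: 4.75 points in the first case, 2.375 in the second. It does not shrink. It is only estimated less precisely.

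**4. Weighting, and whether the heterogeneity test would notice.** As an illustration, pool two studies of 100 per group by inverse variance on the log risk ratio. One is a 7-day study with control risk 11.4% and RR 0.50. The other is a 90-day study with control risk 19% and RR 0.75 or 0.875.

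- 90-day RR 0.75: the 90-day study takes 70% of the weight, pooled RR 0.67, Cochran Q 0.48 on 1 df.
- 90-day RR 0.875: the 90-day study takes 72% of the weight, pooled RR 0.75, Cochran Q 0.93 on 1 df.

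The longer window carries more events and so more weight. At this size the planned heterogeneity test would probably not flag the mix. The illustration borrows a catheter-change rate for one study and a first-passage rate for the other, so it shows the mechanism and is not a forecast.

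**The case against.** Section 4.17 is an extraction list, not a pooling rule. The objective in 3.1 still names procedure-related infection, and the ROBINS-I steps in 4.23 require the outcome to be specified for each study. That is fair, but ROBINS-I judges bias within a study and does not set a window for the pool. A window that is never extracted cannot be used to stratify later.

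The dilution figures depend on late infections being unaffected by prophylaxis. Section 1.5.1 says that colonisation starts as soon as the catheter is placed and leads to biofilm, which leaves room for an effect on later infection, and 3.2 calls the link to colonisation only possible. This stands, and the figures are conditional on the assumption.

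A reader might infer that the review is bound to lean towards finding no benefit, or that a halving of early infections would be undetectable. The documents support neither. No effect measure is named, confounding by indication could move an observational estimate either way, and there is no pooled sample size from which to judge detectability.

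A reader might also infer that benign cases will be pooled, because 4.18 admits studies "even if they contain data on benign obstructive ureteral diseases". But 4.13 and 4.15 confine the question to cancer patients, and 4.17 extracts the number of cancer patients. What remains is a small gap: no rule covers reports that do not separate infections by diagnosis.

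Finally, the literature is sparse, and limiting the review to short windows could leave little beyond the institution's own earlier cohort. That argues for stratifying, not for discarding the longer studies.

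**Conclusion.** The mismatch between 4.17 and 3.1 is established from the text alone: the review's outcome is broader than the objective it serves, and nothing in the plan records or separates the windows. The firm consequence is a pooled estimate that may mix 7-day and 90-day outcomes and is not directly comparable with the cohort.

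Dilution is a plausible further consequence, not a demonstrated one. It applies to risk ratios and odds ratios. It also rests on prophylaxis acting only on early infections, on an assumed early effect, and on an early share that the documents do not supply. Under those assumptions a halving of early infections would show in a 90-day study as anything from a moderate effect to almost none.

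**What to change.** In Section 4.17, replace the any-date wording and add two extraction fields: each study's outcome window and its definition of urinary tract infection.

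In Section 4.22, pre-specify that results are pooled separately by window:

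- The early stratum (7 days, or up to 30 days where that is the shortest window reported) answers the objective in 3.1 and is the one compared with the cohort.
- Longer windows are reported as catheter-related infection.
- The all-dates pool is shown as secondary only.

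Optionally, show studies that do not report infections separately for cancer patients in a sensitivity analysis.

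The cost is a few lines of text and two fields. The price is few studies, and so low precision, in the early stratum. Allowing windows up to 30 days eases this but still mixes 7-day and 30-day outcomes, so the window of each study should be shown on the forest plot. No study is discarded, because longer windows are still reported.
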